### 3.1.2 Dose Escalation

In a phase I/II study (NCT 02649790) that evaluated single agent eltanexor in higher-risk MDS, 2 doses were evaluated: 5 patients received 10 mg and 15 patients received 20 mg, every day for 5 days per week of a 28-day cycle. The majority of patients were aged  $\geq 75$  and all were treated and refractory to hypomethylating agents. None of the patients experienced dose-limiting toxicities (DLTs) and the RP2D for eltanexor was selected as 10 mg given on days 1-5 of each week of a 28-day cycle in HR-MDS (20/28 days). Given the overlap in toxicities, particularly hematologic, between hypomethylating agents and eltanexor, our starting dose was set at 10 mg PO daily on Days 8-12 and Days 15-19 (total of 10 days per 28-day cycle as opposed to 20 days per 28-day cycle in NCT 02649790).

In Phase I, dose escalation will proceed in cohorts of 3-6 participants. The MTD is the dose level at which no more than 1 of up to 6 participants experience DLT during the first cycle (28 days) of treatment, and the dose below that at which at least 2 (of  $\leq 6$ ) participants have DLT as a result of the drug.

Participants in Cohort 1 will be eligible for the DLT evaluation if  $\geq 90\%$  (9 out of 10 doses) of KPT-8602 and  $\geq 80\%$  (4 out of 5 doses) of Inqovi were taken within the DLT period. Participants not evaluable for toxicity, will be replaced in the dose level.

Dose Escalation Schedule	
Dose Level	Dose of KPT-8602
Level -2	5 mg PO daily on Days 8-12 and Days 15-19
Level -1	5 mg PO daily on Days 8-21
Level 1 (starting dose)	10 mg PO daily on Days 8-12 and Days 15-19
Level 2	10 mg PO daily on Days 8-21

Dose escalation will start at dose level 1 and follow the rules outlined in the Table below.

Number of Participants with DLT at a Given Dose Level	Escalation Decision Rule
0 out of 3	Enter up to 3 participants at the next dose level
$\geq 2$	Dose escalation will be stopped. This dose level will be declared the maximally administered dose (highest dose administered). Up to three (3) additional participants will be entered at the next lowest dose level if only 3 participants were treated previously at that dose.
1 out of 3	Enter up to 3 more participants at this dose level. 

• If 0 of these 3 participants experience DLT, proceed to the next dose level.

• If 1 or more of this group suffer DLT, then dose escalation is stopped, and this dose is declared the maximally administered dose. Up to three (3) additional participants will be entered at the next lowest dose level if only 3 participants were treated previously at that dose.

$\leq 1$ out of 6 at highest dose level below the maximally administered dose	This is the MTD and is generally the recommended phase 2 dose. At least 6 participants must be entered at the recommended phase 2 dose.

No new participants will initiate study treatment at the current or next higher (or lower) dose level until the required number of participants have completed DLT evaluation. Each dose-escalation or de-escalation decision will be documented in the study file. The report including the supporting safety data and delineation of each criteria met, with the dose-escalation decisions will be provided to the Sponsor ([[contact]](mailto:[contact])) before additional participants will be enrolled into the study. The Dose Escalation Determination form on the sponsor website: <https://ccrod.cancer.gov/confluence/display/CCRCRO/Forms+and+Instructions> may be used for this purpose.

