## Phase I/II Study Schema

### 3.1.1 Dose Limiting Toxicity (DLT)

The DLT evaluation window will be the first 28 days of study treatment. No dose reductions or interruptions are allowed during the DLT observation period.

A DLT is defined as any of the following treatment-related toxicities (based on CTCAE Version 5.0):

- Any Grade 5 toxicity, unless due to underlying disease, disease progression, or accidental injury.
- Any Grade  $\geq 3$  non-hematologic toxicity, except:
  - Grade 3 or 4 isolated electrolyte abnormalities that resolve, with or without intervention, to Grade  $\leq 2$  within 72 hours
  - Grade 3 nausea, vomiting, or diarrhea that does not require/prolong hospitalization, does not require TPN or NGT feeding, and resolves to Grade  $\leq 2$  within 72 hours
  - Grade 3 fatigue, fever, flu-like symptoms, or headache lasting  $\leq 72$  hours
  - Grade 3 laboratory abnormalities that are not associated with organ pathology
  - Direct complications of cytopenia(s) due to active myeloid malignancy, such as:
    - Grade 3 or 4 febrile neutropenia
    - Grade 3 or 4 infection
    - Grade 3 or 4 hypotension explained by sepsis
    - Grade 3 or 4 hemorrhage/bleeding
- Confirmed Hy's law cases, defined as:
  - AT (ALT or AST) elevation  $> 3$  times upper limit of normal (ULN), AND
  - Total bilirubin  $> 2$  times ULN, without initial findings of cholestasis (elevated serum alkaline phosphatase), AND

- No other immediately apparent possible causes of AT elevation and hyperbilirubinemia, including, but not limited to, viral hepatitis, pre-existing chronic or acute liver disease, or the administration of other drug(s) known to be hepatotoxic.
- In the absence of active MDS, hematologic DLTs for each arm include:
  - any Grade  $\geq 4$  decrease ANC or PLTs lasting more than 28 days.
- Any adverse reaction that leads to dose reduction or withdrawal of KPT-8602.

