### 3.3.1 Dose Levels for Toxicity Management

Dose levels for KPT-8602 (eltanexor) are as follows, for the purposes of toxicity management.

•

Dose level	KPT-8602 dosage
2	10 mg orally once daily on Days 8-21
1	10 mg orally once daily on Days 8-12 and Days 15-19
-1	5 mg orally once daily on Days 8-21
-2	5 mg orally once daily on Days 8-12 and Days 15-19

Dose levels for Inqovi are as follows, for the purposes of toxicity management.

•

Dose level	Inqovi dosage
1	1 tablet orally once daily on Days 1 through 5
-1	1 tablet orally once daily on Days 1 through 4
-2	1 tablet orally once daily on Days 1 through 3
-3	1 tablet orally once daily on Days 1, 3, and 5

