## 10.2 STATISTICAL HYPOTHESIS AND SAMPLE SIZE DETERMINATION

The trial will begin with a phase I dose-escalation phase using a standard 3+3 design which will enroll participants with relapsed/refractory HR-MDS. Up to 18 participants may be enrolled based on the 3+3 design.

Participants will be eligible for the DLT evaluation if  $\geq 90\%$  (9 out of 10 doses) of KPT-8602 and  $\geq 80\%$  (4 out of 5 doses) of Inqovi were taken within the DLT period. Participants not evaluable for toxicity, will be replaced in the dose level.

Phase II will use a Simon's minimal two-stage design, applied separately as noted below:

- Trial will be conducted using a Simon minimax two-stage phase II trial design to rule out an unacceptably low response rate of 25% ( $p_0=0.25$ ) in favor of an improved response rate of 45% ( $p_1=0.45$ ) in order to determine if the combination of KPT-8602 with Inqovi will be able to improve upon an expected 30-40% response rate in participants who have received other agents. With two-sided alpha=0.05 and beta=0.20, the first stage will enroll 21 evaluable participants, and if 0 to 5 of the 21 have a response, then no further participants will be accrued. If 6 or more of the first 21 participants have a response, then accrual would continue until a total of 43 evaluable participants have been treated. If there are only 6-16 participants with a response out of 43 participants, this would be an uninterestingly low response rate. If there were 17 or more of 43 (39.5%) who experienced a response, treatment would be sufficiently interesting to warrant further study in later trials. The probability of early termination under the null (25%) response rate is 56.7%.

It is expected that up to 12-15 participants with MDS may be accrued per year. Thus, in order to accrue up to  $18 + 43 = 61$  participants (which may be reduced by up to 6 if up to 6 participants in phase I may be included in phase II), and to allow for a small number of inevaluable participants (12), it is expected that 3-4 years may be required to accrue the required 73 participants. Note: To allow for screen failures (7), the accrual ceiling will be set at 80 participants for the purposes of the NIH accrual ceiling.

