## 10.3 POPULATIONS FOR ANALYSES

### 10.3.1 Evaluable for toxicity

All participants will be evaluable for toxicity from the time of their first treatment with KPT-8602.

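### The DLT-evaluability rule replaces participants whose DLT stopped KPT-8602 early, so the 3+3 can clear a dose level that is too toxic

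*Combined protocol and SAP*

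**What the plan says.** Section 3.1.2 ties DLT evaluation to exposure alone. A participant needs at least 90% of KPT-8602 doses, glossed as 9 of 10, and at least 80% (4 of 5) "of Inqovi were taken within the DLT period. Participants not evaluable for toxicity, will be replaced in the dose level". Section 10.2 repeats the rule and ends in the same way: "Participants not evaluable for toxicity, will be replaced in the dose level". Neither section keeps a participant in the count because a DLT has occurred.

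Section 3.1.1 sets the window: "The DLT evaluation window will be the first 28 days of study treatment". It adds: "No dose reductions or interruptions are allowed during the DLT observation period". Its list of DLTs closes with "Any adverse reaction that leads to dose reduction or withdrawal of KPT-8602".

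Section 10.3.1 defines the toxicity population differently: "All participants will be evaluable for toxicity from the time of their first treatment with KPT-8602".

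Levels 1 and -2 have 10 KPT-8602 doses per cycle (Days 8–12 and 15–19). Levels 2 and -1 have 14; Section 3.3.1 gives level 2 as "10 mg orally once daily on Days 8-21".

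**The concern.** Stopping KPT-8602 for toxicity is a DLT under 3.1.1. Stopping it early also leaves the participant short of 90% of doses, and 3.1.2 then calls for a replacement. The participants most informative about toxicity are therefore the ones the rule removes. The problem is not confined to the last DLT criterion: any DLT that ends dosing early has the same result, and an early Grade 5 event, read literally, fails the dose count too.

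The Phase I primary endpoint in 10.1 is the RP2D as set by DLT counts per level. Section 10.4.2 also reports the fraction with a DLT at the RP2D. Both are biased downward if DLT participants are dropped, and up to 43 Phase II participants are then treated at the dose selected.

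**Working it through.** **The threshold.** 9/10 = 90% and 4/5 = 80%, so the plan's figures reproduce for the 10-dose levels. They do not carry over to the 14-dose levels: 9/14 = 64.3%, 12/14 = 85.7% (fails) and 13/14 = 92.9% (passes). There, 90% means 13 doses (0.9 × 14 = 12.6).

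**When a permanent stop leads to replacement.**
- 10-dose levels: 3/10 after the Day 10 dose, 5/10 after Day 12, 8/10 after Day 17. All fail. The 9th dose falls on Day 18.
- 14-dose levels: 12/14 after the Day 19 dose fails. The 13th dose falls on Day 20.

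**Effect on the 3+3.** Let p be the true DLT probability at a level and f the share of DLT participants who are replaced. The documents give neither, so both are assumptions and a range is shown. The DLT rate among those counted is

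q = p(1 − f) / (1 − pf).

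Under the table in 3.1.2 a level is cleared with 0/3, or with 1/3 followed by 0/3:

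P(clear) = (1 − q)³ + 3q(1 − q)² × (1 − q)³.

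Example with p = 0.40:
- f = 0: q = 0.40; P = 0.216 + 0.432 × 0.216 = 0.309.
- f = 0.5: q = 0.20/0.80 = 0.25; P = 0.422 + 0.422 × 0.422 = 0.600.
- f = 0.75: q = 0.10/0.70 = 0.143; P = 0.828.

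Chance of clearing the level:

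| True DLT rate | f = 0 | f = 0.25 | f = 0.5 | f = 0.75 | f = 1 |
|---|---|---|---|---|---|
| 20% | 0.709 | 0.798 | 0.887 | 0.964 | 1.0 |
| 33% | 0.434 | 0.557 | 0.714 | 0.890 | 1.0 |
| 40% | 0.309 | 0.428 | 0.600 | 0.828 | 1.0 |
| 50% | 0.172 | 0.265 | 0.428 | 0.709 | 1.0 |
| 60% | 0.082 | 0.141 | 0.265 | 0.551 | 1.0 |

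Simulation at p = 0.50 gave 0.426 for f = 0.5 and 0.710 for f = 0.75, against 0.428 and 0.709 from the formula.

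**Effect on choosing the RP2D.** Section 3.1.2 asks for at least 6 participants at that dose with no more than 1 DLT: P(≤1 of 6) = (1 − q)⁶ + 6q(1 − q)⁵. At p = 0.40 this is 0.047 + 0.187 = 0.233 with correct counting, and 0.178 + 0.356 = 0.534 with half replaced (q = 0.25). At p = 0.33 it goes from 0.358 to 0.661, and at p = 0.50 from 0.109 to 0.351.

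**The case against.** The best defence is that the investigators mean every DLT to count and that the wording is loose. The decision table and the MTD definition in 3.1.2 speak of participants with a DLT, as does the endpoint in 10.1, without restricting this to evaluable participants. The replacement sentence uses the term that 10.3.1 defines, and by that definition nobody treated with KPT-8602 is unevaluable. Section 10.4.4.1 pauses Phase I for review on the 3.1.1 criteria with no dose condition, and 3.1.2 sends a report to the sponsor before further enrolment.

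These texts show a plausible intention but do not repair the rule. The evaluability sentence decides who enters the table, and none of these places states an exception. Taken literally, 10.3.1 leaves no KPT-8602-treated participant to replace, so it contradicts 3.1.2 and 10.2. A pause or a sponsor report applies the counting rule as written; it does not change who is counted.

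Some of the defence stands. Only DLTs that stop KPT-8602 before the threshold dose are lost; later ones count. Section 3.2.1 extends dosing for missed doses, which can rescue a short gap, though not a permanent stop. The values of p and f are assumed, and 3.1.2 reports no DLTs in 20 higher-risk MDS patients (5 at 10 mg, 15 at 20 mg) on single-agent eltanexor, although that was not the combination. The Phase II toxicity monitoring in 10.4.4.1 is a backstop, but it can first act at 3 of 9 participants, after they have received the selected dose. The 14-dose mismatch is minor, because the 90% figure already implies 13 doses.

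**Conclusion.** The concern holds. Followed as written, 3.1.2 and 10.2 remove from the 3+3 any participant whose DLT stops KPT-8602 before the Day 18 dose (levels 1 and -2) or the Day 20 dose (levels 2 and -1). The direction of the bias is certain: the counted DLT rate can only go down.

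Its size depends on the assumed true rate and replaced share. With half replaced, the chance of clearing a level goes from 43% to 71% at a true rate of 33%, and from 31% to 60% at 40%. With only a quarter replaced, it still goes from 43% to 56% at 33%. Because the rule governs the Phase I primary endpoint and the dose taken into Phase II, it should be corrected before escalation decisions rely on it.

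**What to change.** Amend 3.1.2 and 10.2 so that a participant is DLT-evaluable if either:

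- (a) a DLT occurs within the window at any time after the first KPT-8602 dose, whatever number of doses was taken; or
- (b) the window is completed without a DLT, with at least 90% of scheduled KPT-8602 doses (9 of 10, or 13 of 14 on Days 8–21) and at least 4 of 5 Inqovi doses taken.

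Replace only participants without a DLT who do not meet (b). In 10.3.1, separate the general toxicity population from the DLT-evaluable set so that the sections agree. Since the window in 3.1.1 opens with study treatment, the amendment should also say how an event before the first KPT-8602 dose is counted.

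The cost is a few sentences and fewer replacements. A DLT that is now counted may trigger expansion to 6 or de-escalation, which is how a 3+3 is meant to work and stays within the 18 participants planned for Phase I. No dose or treatment rule changes.

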### 3.1.3 Dose Expansion

If no DLTs are observed at the highest planned dose level for evaluation (dose level 2), dose escalation will stop and this will be considered the recommended phase 2 dose (RP2D) of KPT-8602. Phase II may begin once the RP2D has been identified.

### 3.1.4 Protocol Stopping Rules

This study will incorporate stopping rules related to safety and response.

For safety stopping rules, see Section [10.4.4](#).

For response stopping rules, see Section [10.2](#).

### **3.2 DRUG ADMINISTRATION**

Drugs will be self-administered at home except for the days that participants are being seen in clinic for pharmacokinetic blood draws. On those days, participants should be instructed to bring in their medication supply from home, without taking the medication, as they will be instructed when to do so as the blood draws must be timed with drug administration.

#### **3.2.1 KPT-8602**

KPT-8602 will be dosed per participant assignment and as outlined in Section [3.1.2](#). KPT-8602 tablets are film coated for ease in handling and should be swallowed whole (not crushed). Do not break, crush, or divide the tablets to prevent an increased risk of dermatologic toxicity if the powder comes in contact with skin. Oral KPT-8602 should be taken with or within 30 minutes of eating.

Medication bottles and leftover pills will be collected at the end of each cycle to monitor participant adherence.

Participants will be asked to complete a medication diary ([Appendix K](#)). If a dose is missed within 12 hours of the time it is usually administered, administer the missed dose as soon as possible and then resume the normal daily dosing schedule. Extend the dosing period by 1 day for every missed dose to complete the total number of daily doses for each cycle. If a dose is vomited, do not administer an additional dose (continue with the next scheduled dose).

#### **3.2.2 Decitabine and Cedazuridine (Inqovi)**

In both Phase I and Phase II, the study drug of KPT-8602 will be given in combination with standard-of-care (SOC) FDA-approved PO decitabine and cedazuridine (Inqovi).

- Inqovi will be administered via oral route once daily on Days 1-5 of each treatment cycle, according to guidelines outlined in the FDA product label.

The tablet should be taken on an empty stomach, 2 hours before or 2 hours after meals, and at the same time each day.

Tablet should be swallowed whole, and may not be crushed, cut, or chewed.

Participants will be asked to complete a medication diary. If a dose is missed within 12 hours of the time it is usually administered, administer the missed dose as soon as possible and then resume the normal daily dosing schedule. Extend the dosing period by 1 day for every missed dose to complete 5 daily doses for each cycle. If a dose is vomited, do not administer an additional dose (continue with the next scheduled dose).

### **3.3 DOSE MODIFICATIONS**

Participants may continue study treatment if toxicity can be managed by interruption of the dose of study treatment or dose reductions as explained below. The following outlines dose modifications for study-drug related toxicities.

If toxicity is considered to be due solely to one of the study drugs as defined below, the participant may be taken off this drug and after consulting with a Sponsor may continue treatment with the other drug only if the participant is deriving benefit from treatment in the form of stabilization of disease or response.

When, at the beginning of a treatment cycle, treatment delay related to one drug is indicated, treatment with the other drug will be continued. For the purpose of restaging, cycle number will continue to be defined on the basis of a time of 28 days (+/- 7 days), i.e., cycle number will not change due to one drug being held.

Overlapping toxicities may be attributed solely to KPT-8602 if a participant who was already on Inqovi prior to starting on study treatment develops the toxicity upon addition of KPT-8602. In addition, overlapping toxicities may be attributed solely to one of the drugs if dose modification or delay of one drug (while the other is continued at the same dose) results in resolution of the toxicity.

### 3.3.1 Dose Levels for Toxicity Management

Dose levels for KPT-8602 (eltanexor) are as follows, for the purposes of toxicity management.

•

Dose level	KPT-8602 dosage
2	10 mg orally once daily on Days 8-21
1	10 mg orally once daily on Days 8-12 and Days 15-19
-1	5 mg orally once daily on Days 8-21
-2	5 mg orally once daily on Days 8-12 and Days 15-19

Dose levels for Inqovi are as follows, for the purposes of toxicity management.

•

Dose level	Inqovi dosage
1	1 tablet orally once daily on Days 1 through 5
-1	1 tablet orally once daily on Days 1 through 4
-2	1 tablet orally once daily on Days 1 through 3
-3	1 tablet orally once daily on Days 1, 3, and 5

### 3.3.2 Dose Modification Guidelines

#### 3.3.2.1 Criteria for initiation of subsequent cycles

The next cycle of therapy may proceed if the following criteria are met:

##### **Non-hematologic criteria to start the next cycle:**

- Serum Cr < 2 mg/dL
- Serum bilirubin < 2 x ULN
- AST or ALT < 2 x ULN
- No active or uncontrolled infection

Participants who do not meet these non-hematologic criteria should have the next cycle delayed and labs monitored at least weekly. Once resolved, study treatment may resume at the same dose for the next cycle. If not resolved within 4 weeks, dose-reduce when participant meets criteria (as

noted above) to start the next cycle as noted below (if not resolved within 8 weeks participant will be taken off treatment):

Dose reduction	Inqovi dosage*	KPT-8602 dosage*
First	Continue same dose	Reduce by one dose level
Second	Reduce by one dose level	Reduce by one dose level
Third	Reduce by one dose level	Reduce by one dose level
Fourth	Reduce by one dose level	Permanently discontinue

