2.1.1.2 Age  $\geq$ 18 years

2.1.1.3 ECOG performance status  $\leq$  2 (Karnofsky  $\geq$  60%, see [Appendix A](#))

2.1.1.4 Participants must have adequate organ and marrow function as defined below:

- total bilirubin  $\leq$  1.5 X institutional upper limit of normal

OR

$\leq$  3 X institutional upper limit of normal in participants with Gilbert’s syndrome (except for participants with increased bilirubin levels attributed to intramedullary hemolysis, which will be allowable)

- AST(SGOT)/ALT(SGPT)  $\leq$  3 X institutional upper limit of normal

OR

	≤ 5 X institutional upper limit of normal if related to MDS-specific cause
• creatinine clearance (by Cockcroft-Gault)	≥ 60 mL/min/1.73 m 
• QTc(F)	≤ 470 ms

2.1.1.5 Individuals of child-bearing potential (IOCBP) must have a negative serum test at screening. IOCBP is defined as the following:

- Has not undergone a hysterectomy, tubal ligation, or bilateral oophorectomy
- Has not been naturally postmenopausal for at least 24 consecutive months (i.e., has had menses at any time in the preceding 24 consecutive months).

2.1.1.6 Individuals of childbearing potential (IOCBP) as well as those able to father a child with an individual able to become pregnant must agree to use adequate contraception (hormonal or barrier method of birth control; abstinence) unless they have had a prior vasectomy, hysterectomy, or bilateral oophorectomy, prior to study entry, for the duration of study participation, and for at least 6 months after last dose of HMA.

2.1.1.7 Breastfeeding participants must be willing to discontinue breastfeeding from study treatment initiation through 30 days after the last administration of study drug

2.1.1.8 Any prior therapy must have been completed >4 weeks or, if known, ≥ 5 half-lives of the prior agent (whichever is shorter) prior to treatment (with a minimum of 1 week between prior therapy and study treatment). Note: This does not apply to prior HMA therapy if that therapy is Inqovi per Section 2.1.1.1.

2.1.1.9 Ability to understand and the willingness to sign a written informed consent document.

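### The liver criteria for starting each next cycle conflict with the eligibility limits for some participants, with no baseline exception, and the enzyme wording and maximum delay are unclear

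*Combined protocol and SAP*

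**What the plan says.** **Entry.** Section 2.1.1.4 sets AST/ALT at or below "3 X institutional upper limit of normal", with an alternative of "5 X institutional upper limit of normal if related to MDS-specific cause". Total bilirubin must be at or below "1.5 X institutional upper limit of normal", with an alternative of "3 X institutional upper limit of normal in participants with Gilbert’s syndrome" and a further carve-out: "except for participants with increased bilirubin levels attributed to intramedullary hemolysis, which will be allowable". That last allowance has no numeric ceiling.

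**Each next cycle.** Section 3.3.2.1 requires, among other things, "Serum bilirubin < 2 x ULN" and "AST or ALT < 2 x ULN". The consequence of failing is explicit: "Participants who do not meet these non-hematologic criteria should have the next cycle delayed and labs monitored at least weekly". If the value has not resolved in 4 weeks, the dose is reduced once the criteria are met. If it has not resolved in 8 weeks, treatment ends.

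**Baseline allowances elsewhere.** Most of the toxicity tables in Section 3.3.2.2 accept recovery to a stated grade or to baseline. The introduction to those tables limits them to situations other than the next-cycle criteria. The hematologic next-cycle criteria in Section 3.3.2.1 apply only when the marrow shows no active disease. The non-hematologic list has no comparable qualifier.

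**Timing.** Section 3.4.1, under assessment windows, caps the interval between the end of one cycle and the start of the next at 28 days.

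**The concern.** Eligibility deliberately accepts some raised liver values, including values caused by the disease under study. The next-cycle rule then tests the same analytes against a lower number and does not ask whether the value is new. A participant can enter legitimately, complete Cycle 1 with no change in liver tests, and fail the check for Cycle 2 on the value that was accepted at entry. A stable value does not resolve, so the participant moves through the delay rule to removal.

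Three things are at stake. First, an eligible participant may lose treatment for a reason other than toxicity or progression. Section 3.7.1 lists toxicities, with a reference to Section 3.3.2, among the removal reasons, so such a case may be recorded as intolerance. Second, staff may resolve the conflict differently from one participant to the next. Third, in Phase II the first required on-treatment marrow is at the end of Cycle 2 (Section 3.5.2 footnotes). A participant stopped after Cycle 1 might be counted in the response denominator with little opportunity to show a response.

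**Working it through.** **Step 1. Compare the limits, in multiples of ULN.** A conflict exists where the entry ceiling is 2 or more, because the next-cycle limit is strictly below 2.

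| Analyte and entry route | Entry ceiling (2.1.1.4) | Next-cycle limit (3.3.2.1) | Eligible but not meeting the limit |
|---|---|---|---|
| AST/ALT, general | 3 | below 2 | 2 to 3 |
| AST/ALT, MDS-specific cause | 5 | below 2 | 2 to 5 |
| Bilirubin, general | 1.5 | below 2 | none; next-cycle limit is looser by 2 - 1.5 = 0.5 |
| Bilirubin, Gilbert's syndrome | 3 | below 2 | 2 to 3 |
| Bilirubin, intramedullary hemolysis | none stated | below 2 | any value of 2 or more |

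**Step 2. Look for a rescuing clause.** The baseline wording in Section 3.3.2.2 does not reach the next-cycle criteria because of that section's own scope statement. Section 3.3 opens by describing modifications for drug-related toxicity, but the next-cycle list is stated as laboratory values with no attribution test. No other exception was found.

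**Step 3. Read the enzyme line both ways.** If both enzymes must be below 2 x ULN, a participant with either one at 2 x ULN or more is blocked. If one below the limit suffices, only a participant with both at 2 x ULN or more is blocked. For example, ALT of 2.5 with AST of 1.5 fails on the first reading and passes on the second.

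**Step 4. Compare the clocks.** The removal rule is 8 weeks = 56 days. The maximum gap in Section 3.4.1 is 28 days, so they differ by 56 - 28 = 28 days. The resume-at-reduced-dose branch applies to delays of more than 4 weeks (28 days) and up to 8 weeks. If delay is counted from the end of the previous cycle, the 28-day cap leaves no room for that branch. Section 3.4.1 does not say what follows when the cap is exceeded.

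**Step 5. Illustrate a possible effect on Phase II.** Section 10.2 continues with at least 6 responses in 21 and succeeds with at least 17 in 43. With true response rate p:

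P(success) = sum over x = 6 to 21 of P[Bin(21, p) = x] x P[Bin(22, p) >= 17 - x]

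The plan's own figure reproduces: P[Bin(21, 0.25) <= 5] = 0.5666, against the stated 56.7%. At p = 0.45, P(success) = 0.800, matching beta = 0.20.

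Now assume that a fraction f of participants is blocked, all of them are counted, and none responds. The rate becomes 0.45 x (1 - f). The values of f are assumptions; the documents give none.

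| Assumed f | Response rate | P(success) |
|---|---|---|
| 0 | 0.450 | 0.800 |
| 2% | 0.441 | 0.766 |
| 5% | 0.4275 | 0.709 |
| 10% | 0.405 | 0.599 |

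At f = 10%, 0.10 x 43 = 4.3, so about 4 of 43 participants would have to be affected.

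**The case against.** The best defence is that an entry limit and a stricter re-treatment limit can coexist. Section 3.3 is framed around drug-related toxicity, and the next-cycle text speaks of values being resolved, which suits an emergent event better than a stable one. An investigator might reasonably not apply the rule to an unchanged baseline. This shows that a benign reading exists, but the text does not state it. As written, the criteria are numbers, and the explicit baseline wording has been kept out of their reach.

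Other parts of the defence stand and limit the point:

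- A reader might infer that the bilirubin criterion is stricter than eligibility for everyone. It is not. Under the ordinary 1.5 x ULN limit the next-cycle rule is looser.
- A reader might infer that any participant with one enzyme between 2 and 3 x ULN is blocked. That holds only if both enzymes must meet the limit.
- A reader might infer certain removal at 8 weeks, before any marrow. The 28-day cap makes the timing uncertain, and additional marrows are allowed when clinically indicated. Section 3.3 keeps the cycle clock running when one drug is held but does not say what happens when both are.
- A reader might infer a downward bias in the response rate. Section 10.3.2 requires that disease be re-evaluated but does not say whether a blood count alone suffices. If it does not, these participants are inevaluable, and Section 10.2 already allows for 12 such participants.

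**Conclusion.** The conflict is real but limited to two groups: participants enrolled with AST/ALT of 2 to 3 x ULN (to 5 x ULN for an MDS-specific cause), subject to the enzyme ambiguity; and participants enrolled with bilirubin of 2 x ULN or more under the Gilbert's or hemolysis allowance. For them, the rule applied literally can delay and then end treatment with no new toxicity. The ambiguous enzyme line and the mismatch between 8 weeks and 28 days are separate defects in the same rule.

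The size is unknown. The drop in success probability from 0.800 to between 0.766 and 0.599 is illustrative only. It rests on an assumed 2% to 10% of participants being blocked, all of them being counted as evaluable, and none responding. The documents support none of these three assumptions, so no claim of lost power or a biased primary endpoint can be made from them.

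This should be fixed because it bears on who stays on treatment and can arise at the first cycle transition. The documents do not show that the trial's conclusions depend on it.

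**What to change.** In the next amendment, the sponsor should reconcile Sections 2.1.1.4, 3.3.2.1, 3.3.2.2 (its scope statement) and 3.4.1 by stating:

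1. how the non-hematologic next-cycle criteria apply to a participant whose accepted baseline AST, ALT or bilirubin already exceeds them;
2. whether one or both of AST and ALT must meet the limit;
3. which maximum delay governs, and what happens when it is exceeded.

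The clinical limits, and whether a baseline value should count, are for the sponsor's clinicians to decide; this review proposes neither.

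A related statistical clarification would be to say in Section 10.3.2 whether a blood count alone counts as disease re-evaluation. That would settle whether a participant stopped after one cycle enters the response denominator.

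The cost is a few sentences of text, with no added procedures and no change to the sample size.
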